4. Determination that the patient will require prolonged mechanical ventilation possibly requiring muscle relaxation based on the intraoperative course and clinical judgment of the study PI or collaborating intensivists.
5. Intraoperative hypoxia or on arrival to the ICU. (Please see Study Flowchart).
6. Cardiac arrest
7. Sudden arrhythmia (Ventricular tachycardia runs/sudden bradycardia with improper pacemaker detection/function) precluding fast-track extubation protocol.
8. Need for two or more inotrope initiation precluding fast-track protocol. Only a single vasopressor/inotrope may be initiated without excluding the subject.
9. Postoperative ST changes.

10. A positive standard of care pregnancy test during your pre-operative evaluation

9. How will **eligibility** be determined, and by whom?

Eligibility at pre-op and post-op will be based on protocol specific inclusion and exclusion criteria and will be determined by the PI or Sub-I's in collaboration with the ICU attending physician

10. **Risks:** Describe the reasonably foreseeable risks, including risks to subject privacy, discomforts, or inconveniences associated with subjects participating in the research.

Sugammadex is generally safe and well tolerated. Potential risks associated with sugammadex are: hypersensitivity, including anaphylaxis/anaphylactic shock – previous trials suggest this risk is small. Cardiac arrhythmias including bradycardia & tachycardia where intervention is rare and responsive to usual treatment. Other reported risks include nausea, vomiting, constipation.

Bleeding was originally thought to be a side effect, but studies have since showed that Sugammadex falsely elevates the PTT without increasing bleeding risk. (see reference on last page.)

11. **Minimizing Risks:** Describe the way the above-mentioned risks will be minimized.

Patients will all be in a critical care environment and monitored very closely including: blood pressure, heart rate, and chest tube output will be tracked from arrival to the CTICU until extubation per ICU protocol. Subtle changes in the patient's hemodynamic status are easily seen and treated if necessary.

12. **Data and Safety Monitoring Plan:** Include an appropriate Data and Safety Monitoring Plan (DSMP) based on the investigator's risk assessment stated below. (Note: the HIC will make the final determination of the risk to subjects.)

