- a. What is the investigator's assessment of the overall risk level for subjects participating in this study? Greater than minimal risk
- b. If children are involved, what is the investigator's assessment of the overall risk level for the children participating in this study? N/A
- c. Include an appropriate Data and Safety Monitoring Plan

1. Personnel responsible for the safety review and its frequency:

The principal investigator, with the DSMB will be responsible for monitoring the data, assuring protocol compliance, and conducting the safety reviews, which must be conducted at a minimum of every 3 months (including when reapproval of the protocol is sought). During the review process, the principal investigator (monitor) and the DSMB will evaluate whether the study should continue unchanged, require modification/amendment, or close to enrollment. Either the principal investigator, the IRB or DSMB have the authority to stop or suspend the study or require modifications.

2. The risks associated with the current study are deemed greater than minimal for the following reasons: (choose those that apply)

1. We do not view the risks associated with Sugammadex used as neuromuscular blocking reversal agent as minimal risk.
2. Given our experience with the administration of Sugammadex, an FDA approved medication, we do not view the proposed study as high risk.

Although we have assessed the proposed study as one of greater than minimal risk, the potential exists for anticipated and/or unanticipated adverse events, serious or otherwise, to occur since it is not possible to predict with certainty the absolute risk in any given individual or in advance of first-hand experience with the proposed study methods. Therefore, we provide a plan for monitoring the data and safety of the proposed study as follows:

3. Attribution of Adverse Events:

Adverse events will be monitored for each subject participating in the study and attributed to the study procedures / design by the principal investigator [name] according to the following categories:

- a.) Definite: Adverse event is clearly related to investigational procedures(s)/agent(s).
- b.) Probable: Adverse event is likely related to investigational procedures(s)/agent(s).
- c.) Possible: Adverse event may be related to investigational procedures(s)/agent(s).
- d.) Unlikely: Adverse event is likely not to be related to the investigational procedures(s)/agent(s).

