- e.) Unrelated: Adverse event is clearly not related to investigational procedures(s)/agent(s).

4. Plan for Grading Adverse Events:

The following scale will be used in grading the severity of adverse events noted during the study:

1. Mild adverse event
2. Moderate adverse event
3. Severe

5. Plan for Determining Seriousness of Adverse Events:

Serious Adverse Events:

In addition to grading the adverse event, the PI will determine whether the adverse event meets the criteria for a Serious Adverse Event (SAE). An adverse event is considered serious if it results in any of the following outcomes:

1. Death;
2. A life-threatening experience in-patient hospitalization or prolongation of existing hospitalization;
3. A persistent or significant disability or incapacity;
4. A congenital anomaly or birth defect; OR

5. Any other adverse event that, based upon appropriate medical judgment, may jeopardize the subject's health and may require medical or surgical intervention to prevent one of the other outcomes listed in this definition.

An adverse event may be graded as severe but still not meet the criteria for a Serious Adverse Event. Similarly, an adverse event may be graded as moderate but still meet the criteria for an SAE. It is important for the PI to consider the grade of the event as well as its "seriousness" when determining whether reporting to the IRB is necessary.

Only the following adverse events will be tracked. These AE's will trigger an immediate DSMB review; any incidence of anaphylaxis; unexplained hypotension requiring initiation of pressors; cardiac pacing within 5 minutes of drug administration; tachycardia, bradycardia or onset of atrial fibrillation; or increases in chest tube output considered clinically significant by the critical care team. The DSMB will be notified within 2 business days of determination by telephone or email. A written report will be provided within 7 days of the determination. Any incidents meeting SAE criteria will be reported per the IRB reporting policy.

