If the DSMB determines that study drug may be causing an increase in adverse events, the study will be suspended until the DSMB can fully review the events and make a recommendation in consultation with the Yale Human Investigations Committee. The local Merck research representative will also be notified about the events (within 2 business days in case of any serious adverse events). If the data monitoring board and/or IRB view that the study is unsafe, the study will be discontinued.

6. Plan for reporting UPIRSOs (including Adverse Events) to the IRB

The principal investigator will report the following types of events to the IRB:

Any incident, experience or outcome that meets ALL 3 of the following criteria:

1. Is unexpected (in terms of nature, specificity, severity, or frequency) given (a) the research procedures described in the protocol-related documents, such as the IRB-approved protocol and informed consent document and (b) the characteristics of the subject population being studied; AND
2. Is related or possibly related to participation in the research (*possibly related* means there is a reasonable possibility that the incident, experience, or outcome may have been caused by the procedures involved in the research); AND
3. Suggests that the research places subjects or others at greater risk of harm (including physical, psychological, economic, legal, or social harm) than was previously known or recognized.

Unanticipated Problems Involving Risks to Subjects or Others (UPIRSOs) may be medical or non-medical in nature, and include – but are not limited to – *serious, unexpected, and related adverse events and unanticipated adverse device effects*. **Please note** that adverse events are reportable to the IRB as UPIRSOs **only** if they meet all 3 criteria listed above.

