These UPIRSOs/SAEs will be reported to the IRB in accordance with IRB Policy 710, using the appropriate forms found on the website. All related events involving risk but not meeting the *prompt* reporting requirements described in IRB Policy 710 should be reported to the IRB in summary form at the time of continuing review. If appropriate, such summary may be a simple brief statement that events have occurred at the expected frequency and level of severity as previously documented. In lieu of a summary of external events, a current DSMB report can be submitted for research studies that are subject to oversight by a DSMB (or other monitoring entity that is monitoring the study on behalf of an industry sponsor).

7. Plan for reporting adverse events to co-investigators on the study, as appropriate the protocol's research monitor(s), e.g., industrial sponsor, Yale Cancer Center Data and Safety Monitoring Committee (DSMC), Protocol Review Committee (PRC), DSMBs, study sponsors, funding and regulatory agencies, and regulatory and decision-making bodies.

For the current study, the following individuals, funding, and/or regulatory agencies will be notified (choose those that apply):

- All Co-Investigators listed on the protocol.
- Study Grantor (Merck)
- Other Data Safety Monitoring Board (DSMB)
- Yale University IRB

The principal investigator [name] will conduct a review of all adverse events upon completion of every study subject. The principal investigator will evaluate the frequency and severity of the adverse events and determine if modifications to the protocol or consent form are required.

See also DSMB charter attached.

13. Statistical Considerations: Describe the statistical analyses that support the study design.

Variables/Time Points of Interest

The primary outcome is the time to extubation, which will be the duration from arrival to the ICU to the extubation time.

Proposed statistical test/analysis: Positively skewed variables will be log-transformed prior to hypothesis testing. For the primary outcome, a two-sided Student's t-test will be used to compare

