**Adverse Experience Reporting:** Throughout the duration of the study, researchers will adhere to good clinical practice and the guidelines of the institution. Patient vitals will be continuously monitored during and after the administration of the test drug. A data and safety monitoring board (DSMB) consisting of the head nurse and a senior critical care staff will meet monthly to discuss any serious events. Any incidence of anaphylaxis or unexplained hypotension requiring initiation of pressors or cardiac pacing within 5 minutes of drug administration will be reported and evaluated. Increases in chest tube output considered clinically significant by the critical care team will be noted. Any of these adverse events will trigger an analysis by the DSMB. If the DSMB determines that study drug may be causing an increase in adverse events, the study will be suspended until the DSMB is able to fully review the events and make a recommendation in consultation with the Yale Human Investigations Committee. The local Merck research

representative will also be notified about the events. If the data monitoring board and/or institutional review board (IRB) view that the study is unsafe, the study will be discontinued.

**Specific Safety Events to Be Reported During Manuscript Preparation:** For manuscript preparation, the rates of hypotension, anaphylaxis, and bleeding (i.e. Chest Tube output) will be reported and compared between active and placebo groups.

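### The safety plan names no reintubation count by arm, although the benefit sought is earlier extubation

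*Protocol*

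**What the plan says.** The protocol's Data and Safety Monitoring Plan (Section I, 12, item 5) states "Only the following adverse events will be tracked". The list that follows covers anaphylaxis, unexplained hypotension needing pressors, cardiac pacing within 5 minutes of dosing, tachycardia, bradycardia or new atrial fibrillation, and clinically significant rises in chest tube output. These same events trigger immediate DSMB review.

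Other parts of that plan are worded more broadly. Item 3 says "Adverse events will be monitored for each subject participating in the study". In item 7 the principal investigator "will conduct a review of all adverse events upon completion of every study subject", and "The principal investigator will evaluate the frequency and severity of the adverse events".

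Serious events have their own routes. Item 5 says "Any incidents meeting SAE criteria will be reported per the IRB reporting policy" and requires notice to the grantor's local representative "within 2 business days in case of any serious adverse events". Under the SAP's Adverse Experience Reporting section, the DSMB "will meet monthly to discuss any serious events".

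The protocol's Research Plan (Section I, 4) ends participation at successful extubation, without defining success. It places adverse event assessment directly after extubation, without giving its length. The SAP's section on safety events for the manuscript names three for comparison between arms: hypotension, anaphylaxis and bleeding. Both documents also provide a chi-square or Fisher test for categorical adverse events, without naming any.

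**The concern.** The primary outcome rewards a shorter time on the ventilator. The most direct harm of extubating earlier is that the extubation fails and the tube has to go back in. A trial whose title promises both efficacy and safety would be expected to show that count beside the primary result.

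If the tracking sentence is followed literally, reintubation is not collected as a matter of routine. Staff also have no stated period over which to look for it. A reader of the final report could then see the hours gained but not weigh them against failed extubations in each arm.

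A second, smaller matter is that the restriction in item 5 is not reconciled with items 3 and 7. Staff abstracting charts could reasonably follow either rule for a non-serious event that is off the list.

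**Working it through.** **1. The plan's own figure.** The power analysis gives 45 per group for a 2-hour difference, SD 2.89 hours, two-sided alpha 0.05 and 90% power.
- Normal approximation: n = 2 × (1.960 + 1.282)² × (2.89/2)² = 2 × 10.507 × 2.088 = 43.9, so 44 per group.
- Noncentral t: 44.86, so 45 per group, with power 90.1% at 45.

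The stated 45 reproduces, and nothing in this point disputes it. It serves below only as the denominator.

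**2. Where reintubation could be named.**

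| Place | What it covers | Reintubation named? |
|---|---|---|
| Protocol I.12, item 5 list | Anaphylaxis, hypotension, pacing, rate or rhythm events, chest tube output | No |
| SAP, safety events for the manuscript | Hypotension, anaphylaxis, bleeding | No |
| Protocol I.13 and SAP, statistical test | Categorical adverse events in general | No event named |
| Protocol I.12, SAE definition | Death; events that may need intervention to prevent a serious outcome | No, but a case could qualify |
| Protocol I.4, end of participation | Successful extubation, then an assessment of unstated length | No |

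The word does not occur in the text available. Death appears as an SAE criterion but on neither event list.

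**3. The two event lists side by side.** Two items tracked in item 5 are missing from the SAP's comparison list: cardiac pacing within 5 minutes, and tachycardia, bradycardia or atrial fibrillation. The general chi-square or Fisher sentence can cover them, so this is a matter of alignment.

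**4. The scope question.** Item 5 restricts tracking. Items 3 and 7 speak of adverse events without that limit. As an illustration, Section I, 10 says "Other reported risks include nausea, vomiting, constipation"; none of the three is on the item 5 list. With the SAE routes open, the uncertainty is confined to non-serious events off the list.

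**5. What a count could show at 45 per arm.** No event rate is assumed, because the documents give none. Exact (Clopper-Pearson) two-sided 95% intervals:
- 0/45: upper limit 1 − 0.025^(1/45) = 0.0787, so 0% to 7.9%
- 1/45 (2.2%): 0.1% to 11.8%
- 2/45 (4.4%): 0.5% to 15.1%

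For 0/45 against 0/45, the Wilson upper limit in each arm is z²/(n + z²) = 3.84/48.84 = 7.9%. The Newcombe 95% interval for the difference is therefore −7.9 to +7.9 percentage points.

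Fisher's exact test, two-sided: 5 against 0 gives p = 0.056, and 6 against 0 gives p = 0.026. Even if one arm had no events, it would take six in the other to reach 0.05.

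**The case against.** The strongest reply is that the plan already guards against premature extubation and already captures its serious consequences. In both arms, extubation follows a head lift, haemodynamic stability, a 30-minute CPAP trial, a blood gas, and limits on RSBI and tidal volume. The SAP leaves the final decision to the CTICU team, who are kept blind to the neuromuscular measurements. Death is an SAE by definition, and a reintubation could qualify. The SAP's comparison list does not say that it is exclusive, and once recorded, either event could go into the chi-square or Fisher comparison. Tying the end of participation to a successful extubation might also keep a promptly reintubated patient in the study.

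All of this stands as mitigation. It makes a large difference between arms less likely and means that a serious case need not go unseen. It does not commit the trial to a count out of 45 per arm over a fixed period. SAE reporting proceeds case by case and depends on judgment, the general test sentence collects no data, and success of extubation is undefined.

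A further objection is that the flowchart, the DSMB charter and the opening part of the SAP were not available and may name reintubation. That is a real limit, so the request is conditional.

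A reader might infer more: that reintubations and deaths would go unreported, or that the protocol flatly contradicts itself on which events are recorded. The documents support neither. The serious-event routes remain open. The words about all adverse events can be read as all tracked events, and the item 5 list can be read as the triggers for DSMB review. Nausea, vomiting and constipation are also weak examples, since targeted collection for a marketed drug given once is a legitimate choice.

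**Conclusion.** The point holds in limited form. In the text available, neither the tracked list nor the between-arm list names reintubation, and the assessment after extubation has no length. A shorter time to extubation could therefore be reported with no planned count by arm of failed extubations. The tracking sentence is a secondary ambiguity affecting non-serious events off the list.

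The gap is in reporting. It leaves the primary analysis and the sample size unchanged. The missing table could not establish equal safety: no events in either arm would still leave a difference of up to 7.9 percentage points in either direction. Its value is to put the most direct harm beside the benefit with its uncertainty visible.

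The conclusion assumes that the unseen documents do not already provide the count. That reintubation is the harm most directly opposed to the primary outcome is clinical reasoning and is not stated in the documents. The change should be made, but the trial does not depend on it.

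**What to change.** Unless the flowchart, the DSMB charter or the opening part of the SAP already does so:

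1. Add reintubation and death to the events tracked in item 5, and say whether they also trigger immediate DSMB review.
2. Replace the open-ended assessment after extubation with a stated window, chosen by the investigators and the same in both arms.
3. Abstract both events from the ICU chart over that window. Tabulate them by arm, with exact 95% intervals, beside the primary result and labelled descriptive.
4. Align the SAP's between-arm list with item 5 by adding both cardiac pacing within 5 minutes and tachycardia, bradycardia or atrial fibrillation.
5. Reconcile items 3, 5 and 7 so that it is clear whether non-serious events off the list are recorded. Which way to settle this is for the sponsor to decide.

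The cost is some rewording and two extra chart fields for about 90 randomized patients. If the window runs past the current end of participation, an IRB or consent amendment may be needed. No new procedure and no change to the sample size is required.

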2. Patients will be transferred to the CTICU intubated and on a propofol infusion and/or dexmedetomidine (Precedex) from the operating room. Both meds are used SOC.
3. Upon CTICU arrival, the patients surgeon and CTICU intensivist will determine if patient is able to proceed with fast-track extubation. Determination of continued eligibility based on the post-recruitment pre-randomization exclusion criteria will be determined by a member of the study team. Eligible patients will be randomized, investigational pharmacy will be contacted for study drug and within 30 minutes of the ICU admission, propofol will be discontinued. Precedex may be continued per clinical discretion.
4. The participant will be randomized to receive Sugammadex or placebo. The enrolled patients will be assigned to the study and control arms in a 1:1 ratio.
5. IDS will provide the Sugammadex (2mg/kg) vs. Placebo in a syringe. A qualitative train-of-four measurement will be obtained. The administration of the study drug and placebo compounds will be performed by CTICU nurses who will receive the drugs in a blinded fashion from the departmental research pharmacy. The study drug will be supplied by Merck.
6. The clinical care provider has the discretion to determine the appropriate ventilation settings on a case-by-case basis, in accordance with the suggestion that patients will be initiated on SIMV rate of 14 with 60% FiO₂, tidal volumes 8-10 ml/kg and PEEP of 7.
7. Ten minutes after the drug administration, if the patient can lift their head and remains hemodynamically stable, the patient will be switched to CPAP mode of ventilation for 30 minutes. At the end of the CPAP trial tidal volumes, Rapid Shallow Breathing Index (RSBI) and ABG will be assessed. The patient will be extubated if he/she is not hypoxic/ hypercarbic, has RSBI<100 and has TV >300 cc.
8. If a patient fails the 30-minute CPAP criteria, the ICU intensivist will be immediately notified. Every attempt will be made to correct the underlying cause of CPAP failure, and a prompt reassessment will be made as deemed appropriate by the intensivist to reattempt CPAP versus continuing controlled mechanical ventilation.

Study participation will end when the patient is successfully extubated. AE assessment will be performed in the period immediately following extubation.

5. Genetic Testing N/A

6. **Subject Population:** Provide a detailed description of the types of human subjects who will be recruited into this study.

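### No tracked or compared safety item covers being awake and unable to move from residual block, although propofol stops by the clock in both arms and only one arm is reversed

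*Protocol*

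**What the plan says.** **Tracked events.** Protocol Section I, item 12, sub-item 5 states "Only the following adverse events will be tracked". It then names anaphylaxis, unexplained hypotension needing pressors, pacing soon after the drug, tachycardia, bradycardia, new atrial fibrillation, and clinically significant chest tube output. Each triggers immediate DSMB review.

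**Compared events.** Protocol item 13 and the SAP's statistical section compare categorical adverse events by chi-square or Fisher's exact test. The SAP section on safety events for the manuscript names three rates to compare: hypotension, anaphylaxis and bleeding.

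**Risks.** Item 10 begins "Potential risks associated with sugammadex are: hypersensitivity, including anaphylaxis/anaphylactic shock" and continues with arrhythmia, gastrointestinal effects and bleeding. It does not mention residual block.

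**Sedation and block.** Item 4, step 3 says "within 30 minutes of the ICU admission, propofol will be discontinued. Precedex may be continued per clinical discretion". The SAP places the propofol stop 30 minutes after admission. Step 5 says "A qualitative train-of-four measurement will be obtained" and attaches no threshold or action to the result. The first check of strength is in step 7: "Ten minutes after the drug administration, if the patient can lift their head and remains hemodynamically stable". It governs the switch to CPAP. Under Section II, B, item 5, the alternative to reversal is to let the blocking drug wear off.

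**Assessment.** Item 4 ends with "AE assessment will be performed in the period immediately following extubation".

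**The concern.** A patient whose sedation has stopped while the neuromuscular block persists may be awake and unable to move. Under this plan that is possible in either arm before injection, because the order of propofol stop and injection is not fixed. It is more likely to last in the placebo arm, where nothing reverses the block. The documents' only stated mechanism for faster extubation is reversal of block, so residual block at about the time propofol stops is not a remote possibility within the trial's own reasoning.

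What is at stake is the balance of the safety comparison. The tracked list can show possible costs of giving sugammadex. It has no item that directly shows this possible cost of waiting for the block to wear off. If the safety table contains no such event, a reader could not tell whether none occurred or none was recorded.

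**Working it through.** **1. The plan's own figure.** Inputs from item 13: difference 2 hours, SD 2.89, two-sided alpha 0.05, power 90%. The standardised difference is 2 / 2.89 = 0.692. The exact noncentral t calculation gives n = 44.86, so 45 per arm, with power 0.901. The stated 45 reproduces, is not disputed, and is the denominator used below.

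**2. The lists against the event.**
- Protocol tracked list: 7 event types, of which 0 record the event directly. Tachycardia could accompany it but is not specific.
- SAP list of rates to compare: 3 named, of which 0 record it.
- Item 10 risks: not named.

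**3. The sequence of care.**
- The propofol stop is set by time since ICU admission, in both arms.
- Dexmedetomidine is optional and not tied to block.
- A train-of-four is obtained, but no reading is required before propofol stops.
- Head lift gates CPAP, not the propofol stop.
- Only one arm is reversed.

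Followed exactly, the plan therefore allows an interval of wakefulness with residual block. The documents do not say how often it occurs or how long it lasts.

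**4. Other routes by which a case might surface.**
- Item 12, sub-item 3 has adverse events monitored and attributed for each subject.
- Sub-item 7 has the principal investigator review all adverse events after each subject completes.
- Serious events are reported. A distressing but brief episode need not meet the criteria.
- The unanticipated-problem route in sub-item 6 counts psychological harm, but all three of its criteria must be met.
- Related events below the prompt-reporting threshold go into the continuing-review summary.

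None of these names the event, and the word *Only* in sub-item 5 may narrow the first two.

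**5. What adding the item would yield.** The exact (Clopper-Pearson) two-sided 95% upper limit for zero events is 1 − 0.025^(1/n). For x > 0 the limits are the 0.025 quantile of Beta(x, n − x + 1) and the 0.975 quantile of Beta(x + 1, n − x).

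| Reports | 95% limits |
|---|---|
| 0/45 | 0 to 7.9% |
| 1/45 | 0.06% to 11.8% |
| 3/45 | 1.4% to 18.3% |
| 0/90 (both arms) | 0 to 4.0% |

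The chance of at least one report in an arm of 45 is 1 − (1 − r)^45. The rates r are assumed for illustration, with full recall:
- r = 1%: 1 − 0.99^45 = 36%
- r = 2%: 1 − 0.98^45 = 60%
- r = 5%: 1 − 0.95^45 = 90%

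For x versus 0 with 45 per arm, the two-sided Fisher p-value is 2·C(45,x)/C(90,x). For x = 5 this is 0.056, and for x = 6 it is 0.026. With one event in the other arm, 7 versus 1 gives 0.058 and 8 versus 1 gives 0.030. A formal test would rarely be informative, so the result should be descriptive.

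**The case against.** The strongest reply is that a short list of drug-related events is a defensible choice in a 90-patient trial, and that the hazard is inferred and not documented. Several safeguards reduce it. The surgeon and intensivist judge fast-track suitability on arrival. The fourth pre-randomization exclusion removes patients expected to need prolonged ventilation with possible relaxation. Dexmedetomidine may continue, and all patients have standard ICU monitoring. The per-subject monitoring and investigator review are active processes, so a case need not depend only on a patient volunteering it. The proposed question is also imperfect: a yes could reflect sedation, restraint or weakness, and the precision figures above hold for any binary event in 45 patients.

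Most of this stands, and it limits the point to an improvement. It does not remove the gap, because none of these provisions names the event or makes it a data item.

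Four stronger readings are tempting, and the documents do not support them:
- *Nobody asks patients about this.* The content of the assessment after extubation is not described, and the flowchart and DSMB charter were not available. The text shows only that no listed item covers the event.
- *The trial imposes a new risk.* Nothing shows that the timing of the propofol stop departs from usual care.
- *The placebo justification is wrong.* Section II, B, item 5(c) compares placebo with waking outside the study, and nothing contradicts it.
- *The clinical team cannot see the block.* The SAP hides the accelerometer result. The qualitative train-of-four is not stated to be hidden.

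**Conclusion.** The point holds as a low-cost safety improvement, not as a demonstrated error. The closed tracked list and the SAP's list of rates to compare both omit being awake and unable to move from residual block, while the care sequence leaves that event possible and treats the arms differently with respect to it. As written, the comparison of harms would not systematically include it, so its absence from the results would not be evidence that it did not happen.

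The frequency of the event cannot be given from the documents, and the 1%, 2% and 5% rates above are illustrations. The conclusion rests on reading *Only* as limiting what is collected and on the unseen attachments not already adding the item. The sample size and the primary analysis are unaffected.

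**What to change.** 1. Add an item such as *awake and unable to move before extubation (possible residual block)* to the tracked events in Protocol Section I, item 12, sub-item 5, and to the SAP's list of safety rates for the manuscript. Changing the Protocol alone would leave the SAP list without it.
2. At the assessment already planned after extubation, ask one standard question in both arms under blinding, for example: *Before the breathing tube came out, were you ever awake, trying to move, and unable to?* State that tube discomfort alone does not count.
3. Read each report alongside the train-of-four and any accelerometer readings, noting that these cannot date the recollection.
4. Report counts by arm with exact 95% limits, labelled descriptive.
5. Send the reports to the routine DSMB safety reviews, "which must be conducted at a minimum of every 3 months", and exempt them from the immediate trigger unless they meet serious-event criteria.

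A short mention in item 10 is optional. Section II, B, item 5(c) need not change.

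The cost is one question, one row in the safety table and brief wording changes in two places, with no change to sample size or treatment. The downsides are that recall soon after sedation may be incomplete, and that a yes may reflect sedation, restraint or weakness and not block.
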